7.3.2 Method of Detecting Adverse Events and Serious Adverse Events

The methods of recording, evaluating and assessing seriousness, causality and severity of AEs and SAEs are described in [Appendix 12.4 Adverse Events: Definitions and Procedures for Recording, Evaluating, Follow-up or Reporting]. Care will be taken not to introduce bias when detecting AEs and/or SAEs. Open-ended and nonleading verbal questioning of the subject is the preferred method to inquire about AE occurrences.

An AE with a change in severity is recorded as a new AE.

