5.4 Safety Endpoints

Safety endpoints including adverse events (AEs), laboratory test, vital signs, 12-lead electrocardiogram (ECGs) and Eastern Cooperative Oncology Group (ECOG) performance status are secondary endpoints of the study.

Safety will be assessed by evaluation of the following variables:

- Treatment-emergent adverse events (TEAEs; frequency, severity, seriousness, and relationship to study drug).
 - TEAE is defined as an adverse event observed after starting administration of the study drug and within 30 days after taking the last dose of study drug. For serious AEs in Cohort 9, TEAE definition is revised to within 90 days after the last dose of either study drug. If the adverse event occurs on the first dose date and the onset check box is marked “Onset after first study drug taken” or the onset check box is left blank, then the adverse event will be considered treatment emergent. If the adverse event occurs on the first dose date and the onset check box is marked “Onset before first study drug taken”, then the adverse event will not be considered treatment emergent. If a subject experiences an event both during the pre-investigational period and during the investigational period, the event will be considered as TEAE only if it has worsened in severity (i.e., it is reported with a new start date). If a complete onset date is unknown, and the onset check box is marked “Onset after first study drug taken”, then the adverse events will be considered treatment emergent. If the onset check box is marked “Onset before study drug taken”, then the adverse event will not be considered treatment emergent. If onset check box is left blank, imputed onset date as specified in Section 6.9.2 will be used to determine whether an adverse event is treatment emergent.
 - A drug-related TEAE is defined as any TEAE with relationship to study drug (enfortumab vedotin or pembrolizumab) marked as “Yes” on eCRF as assessed by investigators or with missing assessment of the causal relationship.
- Serious adverse events (SAEs) include adverse events that are flagged as serious by the investigator on eCRF, or with missing serious assessment on eCRF, or upgraded by the Sponsor based on review of the Sponsor’s list of Always Serious term or the important medical event process.
- Adverse events of special interest for enfortumab vedotin (AESI)

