 - For cohorts 1 to 9, hyperglycemia, peripheral neuropathy, dry eye, corneal disorders and blurred vision, skin reactions, and infusion related reactions are considered adverse events of special interest (AESI) for enfortumab vedotin. These are medical concepts of composite terms based on the search criteria utilizing MedDRA terminology (standard MedDRA query [SMQ], sponsor specific query [SSQ], customized MedDRA query [CMQ], high level group term [HLGT], high level term [HLT], preferred term [PT]). Other AEs may be added as AESI as necessary due to ongoing pharmacovigilance activities. The search criteria for AESI will be maintained in a separate document and finalized prior to database lock.
 - For selected AESI, time to onset of AESI will be calculated. Time to first onset of a specific AESI will be calculated as the time from the first dose of study drug to the onset of the first treatment-emergent adverse event that meets the respective search criteria.

- For selected AESI, time to resolution of AESI will be calculated. Resolution is defined as event outcome of ‘recovered/resolved’ or ‘recovered/resolved with sequelae’. For treatment-emergent events with an outcome of ‘recovered/resolved’ or ‘recovered/resolved with sequelae’, time to resolution will be calculated as time from the event onset date to end date.

Time to resolution is defined at the event level. AE records that belong to the same event will be linked.

- Other AEs of risk for enfortumab vedotin
For cohorts 1 to 9, pneumonitis/interstitial lung disease (ILD) is defined as other AEs of risk for EV. Similar as AESI, terms are based on the search criteria utilizing MedDRA terminology.
- Adverse events of special interest for pembrolizumab (AEOSI)
 - For cohort 9, AEOSI are immune-mediated events and infusion-related reactions, following the Keytruda AEOSI List which is a pre-specified list of preferred terms (PTs) developed by MSD to consistently characterize the nature and frequency of each AEOSI across the clinical program, regardless of causality as reported by investigators. These PTs are considered to be medically equivalent to the identified risks for pembrolizumab. The list of PTs may be updated by MSD based on emerging pembrolizumab safety data or as a result of MedDRA updates.
- Clinical laboratory variables

Below is a table of the laboratory tests that will be performed during the conduct of the study.

Panel/Assessments	Parameters to be Analyzed	NCI-CTCAE Grading (Hyper/Hypo)

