5.5 Other Endpoints

5.5.1 Cohorts 1 to 8

- Duration of exposure (months)

Duration of exposure = [min (last date of exposure, death, cutoff date) – first dose date +1] / 30.4375

Last date of exposure = (initial dose date of the last cycle + 28 -1)

- Number of cycles

Total number of cycles with non-zero dosing

- Cumulative dose (mg)

Sum of (total dose administered) across all days

Total dose administered on a dosing day (mg) = final concentration (mg/mL) * actual volume administered (mL)

- Planned dose intensity (mg/kg/cycle)

Initial dose of enfortumab vedotin multiplied by planned number of dosing days per cycle.

For example, subject is planned to receive enfortumab vedotin at a dose of 1.25mg/kg on days 1, 8, 15 of each cycle, the planned dose intensity = 1.25mg/kg * 3 = 3.75 mg/kg per cycle.

- Dose intensity (mg/kg/cycle)

$$\frac{\sum_{i=1}^{NC} \sum_{j=1}^3 (TD_{i,j}/W_{i,j})}{(last\ date\ of\ exposure - first\ dose\ date + 1)/28}$$

where, $TD_{i,j}$ is the actual total drug administered at cycle i day j ,

$W_{i,j}$ is the body weight recorded at cycle i day j ,

NC is the number of cycles with non-zero dosing.

If body weight >100 kg, then $W_{i,j}$ = 100 kg. If there is no dose administered on a planned dosing day in a cycle, then $TD_{i,j}$ = 0 mg.

- Relative dose intensity (%)

$$\frac{Dose\ intensity}{Planned\ dose\ intensity} \times 100$$

5.5.2 Cohort 9

For enfortumab vedotin:

- Duration of exposure (months)

Duration of exposure = [min (last date of exposure, death, cutoff date) – first dose date +1] / 30.4375

Last date of exposure = (initial dose date of the last cycle + 21 -1)

- Number of cycles

Total number of cycles with non-zero dosing

- Cumulative dose (mg)

Sum of (total dose administered) across all days

Total dose administered on a dosing day (mg) = final concentration (mg/mL) * actual volume administered (mL)

- Planned dose intensity (mg/kg/cycle)

Initial dose of enfortumab vedotin multiplied by planned number of dosing days per cycle.

For example, subject is planned to receive enfortumab vedotin at a dose of 1.25mg/kg on days 1, 8 of each cycle, the planned dose intensity = 1.25mg/kg * 2 = 2.5 mg/kg per cycle.

- Dose intensity (mg/kg/cycle)

$$\frac{\sum_{i=1}^{NC} \sum_{j=1}^2 (TD_{i,j}/W_{i,j})}{(last\ date\ of\ exposure - first\ dose\ date + 1)/21}$$

where, $TD_{i,j}$ is the actual total drug administered at cycle i day j,

$W_{i,j}$ is the body weight recorded at cycle i day j,

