6.5.1 Adverse Events

All adverse events recorded on treatment including within 30 days from the last study treatment, or within 90 days from the last study treatment for SAEs in Cohort 9 will be summarized.

Summaries and listings of SAEs include SAEs upgraded by the sponsor based on review of the Sponsor's list of Always Serious terms or the important medical event process if any upgrade was done.

The coding dictionary for this study will be MedDRA. It will be used to summarize AEs by SOC and PT. AEs will be graded using National Cancer Institute's Common Terminology Criteria for AEs (NCI-CTCAE).

The definition of TEAEs leading to treatment discontinuation, TEAEs leading to interruption of treatment and TEAEs leading to dose reduction is listed below. The rules will be followed in the applicable TEAE analyses.

- TEAEs leading to permanent discontinuation of study drug is defined as TEAEs leading to withdrawal of any study drug (enfortumab vedotin or pembrolizumab) in Cohorts 1-9. TEAEs leading to permanent discontinuation of enfortumab vedotin is defined as TEAEs leading to withdrawal of enfortumab vedotin in Cohort 9. TEAEs

leading to permanent discontinuation of pembrolizumab is defined as TEAEs leading to withdrawal of pembrolizumab in Cohort 9.

- TEAEs leading to dose interruption is defined as TEAEs leading to interruption of any study drug (enfortumab vedotin or pembrolizumab) in Cohorts 1-9. TEAEs leading to interruption of enfortumab vedotin is defined as TEAEs leading to interruption of enfortumab vedotin in Cohort 9. TEAEs leading to interruption of pembrolizumab is defined as TEAEs leading to interruption of pembrolizumab in Cohort 9.
- TEAEs leading to dose reduction is defined as TEAEs leading to reduction of enfortumab vedotin in Cohorts 1-9. Pembrolizumab reduction is not allowed.

An overview table to report the number and percentage of subjects and another overview table to report number of events and events adjusted by patient year of drug exposure will include the following details by cohort and overall:

- Number and percentage of subjects with TEAEs,
- Number and percentage of subjects with drug-related TEAEs,
- Number and percentage of subjects with serious TEAEs,
- Number and percentage of subjects with serious drug-related TEAEs,
- Number and percentage of subjects with TEAEs leading to permanent discontinuation of study drug,

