- drug-related TEAEs leading to dose reduction,
- TEAEs leading to dose interruption,
- TEAEs leading to interruption of enfortumab vedotin,
- TEAEs leading to interruption of pembrolizumab,
- drug-related TEAEs leading to dose interruption,
- drug-related TEAEs leading to interruption of enfortumab vedotin,
- drug-related TEAEs leading to interruption of pembrolizumab,
- grade 3 or higher TEAEs,
- grade 3 or higher drug-related TEAEs,
- TEAEs leading to death,
- drug-related TEAEs leading to death,
- TEAEs leading to death excluding disease progression,
- drug-related TEAEs leading to death excluding disease progression,
- Common TEAE that equal to or exceed a threshold of 5% in any cohort (excluding serious AEs)

The number and percentage of subjects with TEAEs, as classified by PT only, will be summarized for each cohort and overall for the following:

- TEAEs,
- drug related TEAEs,
- serious TEAEs,
- drug related serious TEAEs,
- grade 3 or higher TEAEs,
- grade 3 or higher drug-related TEAEs,
- TEAEs leading to permanent discontinuation of study drug,
- TEAEs leading to permanent discontinuation of enfortumab vedotin,
- TEAEs leading to permanent discontinuation of pembrolizumab,
- drug related TEAEs leading to permanent discontinuation of study drug,
- drug related TEAEs leading to permanent discontinuation of enfortumab vedotin,
- drug related TEAEs leading to permanent discontinuation of pembrolizumab,
- TEAEs leading to dose reduction,
- drug-related TEAEs leading to dose reduction,
- TEAEs leading to dose interruption,
- TEAEs leading to interruption of enfortumab vedotin,
- TEAEs leading to interruption of pembrolizumab,
- drug-related TEAEs leading to dose interruption,
- drug-related TEAEs leading to interruption of enfortumab vedotin,
- drug-related TEAEs leading to interruption of pembrolizumab,
- TEAEs leading to death,
- drug-related TEAEs leading to death

AE summary tables will include subject counts as opposed to AE counts. If a subject experiences more than one episode of a particular AE, the subject will be counted only once for that event. If a subject has more than one AE that code to the same preferred term, the subject will be counted only once for that preferred term. Similarly, if a subject has more than one AE within a body system, the subject will be counted only once for that body system.

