		Add additional subgroup analysis based on prior use of anti-cancer therapy and best response to selected prior anti-cancer therapy	
months, thus the sensitivity analysis will not provide additional information
 
 • Exploratory analysis for biomarker including Nectin-4 will be described in a separate biomarker SAP • Add additional subgroup analysis for prior anti-cancer therapy to cover different standard of care treatment for different cancer types.
		
Section 6.5
 
Add overview of AE table to report number of events and events adjusted by patient year
 
Add summaries for overview and by SOC and PT for TEAE and drug-related TEAE leading to death excluding disease progression
 
Add summaries for SAE, >=Grade 3 TEAE, TEAE leading to discontinuation, TEAE leading to dose reduction, TEAE leading to dose interruption by descending frequency of PT
 
Add summaries for serious AESI, AESI leading to discontinuation of study drug, AESI leading to dose reduction, AESI leading to dose interruption.
 
Clarify analysis for laboratory evaluation and definition of treatment-emergent grade 3 or 4 laboratory results
 
Clarify ECG interpretation category
	
 • Add AE analysis by patient year to adjust for potential difference in drug exposure across different cohorts • Add these analyses to exclude death due to disease progression • Add these analyses to help identify the most common PTs in each category • Add additional summaries for AESIs to better characterize identified or potential risk of study drug • Apply same window as TEAE to treatment-emergent laboratory toxicity • To be consistent with information collected on eCRF
		
Section 6.6
 
Update Table 2 to include Cohort 7 and Cohort 8
	Per updates in protocol amendment 2
		
Section 6.8
 
Update timing of primary analysis for each cohort
	Due to enrollment separation of different cohort, primary analysis will be conducted for each cohort
3.0	4-Oct-2023	Section 2.1	Based on clinical data from cohort 5 in the current study, the

Version	Date	Changes	Comment/rationale for change

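### The adverse event rate per patient-year counts events over a longer period than its exposure denominator covers, which inflates the rate most where treatment is short

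*SAP*

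**What the plan says.** **The table.** Beside the overview of subjects with events, SAP 6.5.1 plans "another overview table to report number of events and events adjusted by patient year of drug exposure", by cohort and overall. SAP section 7 gives the reason: "Add AE analysis by patient year to adjust for potential difference in drug exposure across different cohorts".

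**What is counted.** Under SAP 5.4 an event is treatment-emergent if it is seen after dosing starts and "within 30 days after taking the last dose of study drug". There is one extension: "For serious AEs in Cohort 9, TEAE definition is revised to within 90 days after the last dose of either study drug".

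**What it is divided by.** SAP 6.5.1 does not define a patient-year of drug exposure. The only exposure definition is the duration of exposure in SAP 5.5. It runs from first dose to the earliest of the last date of exposure, death and cutoff. For Cohorts 1 to 8, "Last date of exposure = (initial dose date of the last cycle + 28 -1". For each drug in Cohort 9, 21 replaces 28. Interruptions are not subtracted.

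**The counting unit.** Protocol 7.3.2 states: "An AE with a change in severity is recorded as a new AE". The SAP says "AE records that belong to the same event will be linked", but only under time to resolution of events of special interest. Its general rule in 6.5.1 is "AE summary tables will include subject counts as opposed to AE counts", which cannot govern a table of event counts.

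**The concern.** A rate per unit of person-time is interpretable when every event that can enter the numerator falls in time that enters the denominator. Here the numerator window outlasts the exposure period by a number of days that depends on the day of the last dose, not on how long the subject was treated. The excess is therefore a large share of a short exposure and a small share of a long one.

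The table was added to remove exposure differences between cohorts, and this mismatch puts part of them back. A cohort that progresses early and stops after a few cycles would look more toxic per year than a longer-treated cohort with the same underlying rate.

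The uncovered days need not be quiet. Protocol 7.3.5 requires every death within 30 days of the final dose to be reported as a serious adverse event, even when attributed to progression. The rows in SAP 6.5.1 that exclude disease progression exist only for events leading to death, not for all or all serious events.

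**Working it through.** The documents give no exposure-adjusted rate and no expected exposure by cohort, so there is no figure of the plan's own to reproduce. What follows is a day count from the definitions, with treatment length assumed.

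**Inputs.** Cycle length is 28 days with doses on days 1, 8 and 15 (Cohorts 1 to 8), or 21 days with enfortumab vedotin on days 1 and 8 and pembrolizumab on day 1 (Cohort 9). The counting window is 30 days, or 90 days for Cohort 9 serious events (SAP 5.4). Exposure ends on the last day of the last cycle (SAP 5.5.1, 5.5.2).

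**Days without person-time.** If the last dose is on day d of the last cycle, the gap w is:

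- Cohorts 1 to 8: w = d + 30 − 28, which is 3, 10 or 17 days for d = 1, 8 or 15.
- Cohort 9, all events: w = d + 30 − 21, which is 10 or 17 days for d = 1 or 8.
- Cohort 9, serious events: w = d + 90 − 21, which is 70 or 77 days for d = 1 or 8.

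**Inflation.** Let D be the exposure in days (28 or 21 times the number of cycles). At a constant event rate, the reported rate divided by the rate on matched time is (D + w)/D.

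| Cohorts 1 to 8 | D (days) | last dose day 1 (w = 3) | day 8 (w = 10) | day 15 (w = 17) |
|---|---|---|---|---|
| 1 cycle | 28 | 1.11 | 1.36 | 1.61 |
| 2 cycles | 56 | 1.05 | 1.18 | 1.30 |
| 6 cycles | 168 | 1.02 | 1.06 | 1.10 |
| 12 cycles | 336 | 1.01 | 1.03 | 1.05 |

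**Effect on a comparison of 2 cycles with 6 cycles, same true rate.**

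- Last dose on day 15: (73/56)/(185/168) = 1.304/1.101 = 1.18. A true rate of 10 per patient-year would be reported as 13.0 and 11.0.
- Last dose on day 1: (59/56)/(171/168) = 1.054/1.018 = 1.035.
- Last dose on day 15 with half the event rate in the gap: (64.5/56)/(176.5/168) = 1.152/1.051 = 1.10.

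**Cohort 9, last dose on day 8.**

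- All events: 38/21 = 1.81 at 1 cycle and 185/168 = 1.10 at 8 cycles.
- Serious events: (21 + 77)/21 = 4.67 at 1 cycle, (84 + 77)/84 = 1.92 at 4 cycles, and (168 + 77)/168 = 1.46 at 8 cycles.

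The serious-event ratios are upper bounds. Protocol 7.3.1 extends collection to 90 days only for serious events related to pembrolizumab, and 7.3.5 adds deaths. Most of the extra window is therefore not open to every serious event.

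**The case against.** **The denominator already contains off-drug time.** A reader might infer that the table divides by on-drug time only. The SAP does not support that. Exposure is credited to the end of the last cycle and includes interruptions, so after a last dose on day 15 there are already 13 further days in the denominator. If exposure did end at the last dose, the one-cycle ratio would be 45/15 = 3.00 instead of 45/28 = 1.61.

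**The 18% is near the worst case.** It needs every last dose on day 15, survival to day 30, no truncation and an unchanged event rate off drug. The gap is zero for subjects on treatment at cutoff. Death shortens it, as does new anticancer therapy in Cohorts 1 to 8, where Protocol Table 1 footnote 8 ends collection (7.3.1 does not repeat this limit). Early progressors may well be the ones who start new therapy. Delayed cycles lengthen exposure while leaving the gap unchanged. All of this stands, and is why a range is given.

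**Each severity change may not be a separate event.** A reader might infer from Protocol 7.3.2 that one episode moving from grade 1 to 2 and back counts three times. That is a rule for recording data. The SAP distinguishes records from events but does not say which this table counts. The gap in specification is real, but triple counting is not the stated plan, and nothing ties it to short treatment.

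**The table is minor.** It is descriptive, the other adverse event summaries count subjects, and the decision rule in SAP 6.7 uses responders. Events per year of exposure, rather than per year at risk, is also partly a choice of estimand. This lowers the stakes. It does not make a numerator and denominator over different periods suitable for comparing cohorts.

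**Conclusion.** The mismatch is real and follows from the SAP's own definitions, provided that patient-years of drug exposure means the duration of exposure in SAP 5.5, the only definition given. In Cohorts 1 to 8 up to 17 days per subject can contribute events without person-time. In Cohort 9 it is up to 17 days for all events and up to 77 days for serious events.

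The bias always favours longer-treated cohorts. Between 2 and 6 cycles it runs from about 3.5% to 18% at a constant event rate, and lower if events are rarer off drug. These sizes are illustrative, because the documents give no treatment duration by cohort. The Cohort 9 serious-event row is the most exposed. It also sets a 90-day numerator beside 30-day numerators and pools them in the overall column.

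The point merits a change because the table exists to compare cohorts and the correction is cheap. No efficacy conclusion or stopping decision depends on it.

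**What to change.** In SAP 6.5.1, define the denominator as patient-years at risk. It should run from first dose to the earliest of the end of the applicable counting window, death, data cutoff and end of adverse event collection. The window ends at last dose + 30 days, or last dose of either drug + 90 days for Cohort 9 serious events. This also settles the Cohort 9 denominator: SAP 6.3.2 summarises exposure to enfortumab vedotin, pembrolizumab and any drug, 6.5.1 does not say which applies, and 5.5.2 has no formula for any drug.

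Alternatively, keep the exposure denominator and count only events with onset within the defined exposure period.

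The cost is SAP wording and programming from dates already collected, plus a second person-time variable for Cohort 9 serious events. The rates become less directly comparable with tables based on drug exposure alone. Because days 31 to 90 in Cohort 9 collect only pembrolizumab-related serious events and deaths, the longer denominator will dilute the rate of other serious events. A footnote should say so.

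As a secondary clarification, state whether the event count uses adverse event records or linked events. Linking would have to be extended from the events of special interest to all treatment-emergent events.

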6.5.2 Clinical Laboratory Evaluation

The baseline value will be the last nonmissing value taken on or prior to first dose of study drug.

Quantitative values evaluated by local laboratories including hematology, biochemistry, and urinalysis will be summarized using mean, standard deviation, minimum, maximum and median by cohort and overall at each analysis visit. Additionally, a within-subject change will be calculated as the postbaseline measurement minus the baseline measurement and summarized in the same way. Plots of median, 25th percentile, and 75th percentile lab values at each scheduled assessment time will be provided for each laboratory parameter by cohort and overall.

Laboratory results will be graded using NCI-CTCAE, where possible. Parameters that have criteria available for both low and high values, i.e., hypo- and hyper-, will be summarized for both criteria. The same subject can be counted for both values if the subject has different

laboratory values meeting each criterion. NCI-CTCAE grade of laboratory evaluations will be summarized by number and percentage of subjects for each visit. Shift tables of NCI-CTCAE grade change from baseline to worst postbaseline grade for selected laboratory parameters will also be presented. The number and percentage of subjects with treatment-emergent NCI-CTCAE grade 3 or 4 laboratory results will be summarized by cohort and overall. Treatment-emergent NCI-CTCAE grade 3 or 4 laboratory results are defined as: subject's worst postbaseline NCI-CTCAE grade for a laboratory parameter being grade 3 or 4, and the worst postbaseline grade is higher than subject's baseline grade for that laboratory parameter. If baseline grade is missing, any postbaseline grade 3 or 4 laboratory result is considered as treatment-emergent. When determining the worst postbaseline value for a subject, both scheduled and unscheduled lab results collected within 30 days after the last dose of study drug will be included.

Laboratory data will be displayed in listings.

